STUDY PROTOCOL

NCT03223883

Aug 19, 2024

STUDY DESIGN

- **Study Subjects:** A total of 88 individuals (age 45-74 years) with stage IIIb and IV CKD will be recruited. Inclusion and exclusion criteria are shown in **Table 1** and discussed in the **Protection of Human Subjects** section. Estimated GFR will be calculated based on the 4- variable Modification of Diet in Renal Disease (MDRD) formula ¹. After obtaining informed consent, individuals with estimated GFR 15-45 mL/min/1.73m² who fulfill the inclusion and exclusion criteria will be included in the study. We chose an estimated GFR cut-off of <45 mL/min/1.73m² (stage IIIB) for the inclusion in the study based on data by [name] that indicate the prevalence of cognitive impairment is significantly increased when estimated GFR is <50 mL/min/1.73m²². All subjects will be required to have adequately controlled blood pressure (BP), as our hypothesis is that curcumin reduces vascular dysfunction by targeting non-traditional risk factors for CVD. Adequately controlled BP will be defined as BP <140/90 mmHg in accordance with the current Joint National Committee guidelines ³. However, if the guidelines change for older adults without DM (based on the recent evidence from Systolic Blood Pressure Intervention Trial (SPRINT) ⁴), then we would require a systolic BP <120 mmHg for those patients.

Inclusion Criteria	Exclusion Criteria
Age 45-74 years old	Consuming a diet rich in curcumin or taking curcumin supplements in the past 12 months
CKD stage IIIb and IV	Life expectancy <1 year
(estimated GFR: 15-45 mL/min/1.73m ²)	
BMI <35 kg/m ^{2 5}	Pregnant, breastfeeding,
	or unwilling to use adequate birth control
Able to give informed consent	Uncontrolled hypertension
	Severe liver disease
	Severe congestive heart failure
	Hospitalization within the last 3 months
	Active infection or antibiotic therapy
	Immunosuppressive therapy within the last year

Table 1: Inclusion and exclusion criteria

We will also screen for the use of supplements that may improve vascular function including vitamins C and E ⁶ and resveratrol ⁷. Subjects who are taking these supplements but otherwise qualify for the study will be asked to undergo a 6-week wash-out period prior to participating in the study.

- **Experimental Design:** 88 subjects, recruited at the University of Iowa Hospitals and Clinics (UIHC) and The Iowa City VA Medical Center, will be randomized to receive either placebo or curcumin (2000 mg/ day) for 12 months and stratified randomization will be employed based on age \geq 55 yeas ⁸⁻¹⁰ and baseline DM status ¹¹. Block randomization is an alternative for consideration. Study outcomes will be evaluated at baseline, 6 months, and 12 months (except cognitive function will be evaluated at baseline and 12 months only).

- **Curcumin supplementation:** Based on our preliminary data we will use a solid lipid curcumin particle (SLCP, Longvida, Verdure Sciences) at a dose of 2000 mg/d. Based on our preliminary data, we believe this will be an effective dose to improve vascular function in patients with CKD. Longvida will provide the supplement in addition to identical-looking placebo. The randomization table will be generated by [name] and provided to Longvida. Once a subject is randomized, Longvida will package and ship the study drug (curcumin or placebo). The package will only state "study drug" in order to guarantee blinding of all the study staff and participants. As we show in the **Preliminary Data** and **Protection of Human Subjects** sections, curcumin was well-tolerated with a small number of adverse events (mainly gastrointestinal discomfort).

- **Rational for the duration of the study:** In specific aim 2, we intend to evaluate whether curcumin improves cognitive function in patients with CKD. Although our preliminary data suggests that curcumin may improve cognition in as little as 12 weeks, we believe a longer duration is necessary to minimize practice effects from repeated cognitive testing ^{12,13}. Thus, the study duration will be 12 months. In addition, this longer duration will

enhance our ability to detect a benefit on vascular stiffness (specific aim 1). Large elastic artery stiffness reflects structural changes of the extracellular matrix in the vessel wall ¹⁴. Based on this, the longer duration of study will allow the treatment to reverse these structural changes in the vasculature. The vascular measurements will be conducted at baseline, 6 months, and 12 months. In order to reduce practice effects, cognitive function will be measured at baseline and 12 months only.

- **Recruitment Clinics:** The trial will be conducted through CRU of the ICTS at UIHC. Patients will be recruited from 2 clinics with access to >1500 CKD patients from all over the Iowa State area including:

1) UIHC Renal Clinic: The renal clinics at UIHC see approximately 3600 patient visits annually. At least 2500 patient visits are related to stage III/IV CKD. This is a similarly-sized practice to the prior proposal.

2) Iowa City VA Medical Center: The VA renal clinics see approximately 1950 patient visits annually the majority of whom have underlying stage 3 and 4 CKD.

Based on the preliminary screening of our database at the UIHC, we expect at least 100 eligible patients per year. Notably, [name] has been successful in recruiting patients with CKD to clinical trials, including single center, completing recruitment prior to end of funding period on corresponding grant applications. Additionally, UIHC has been a successful site of recruitment for clinical researchers at the University of Iowa (for example [name]).

- Detailed sessions: The study design is illustrated in Figure A.

(All study procedures will be conducted at UIHC Clinical Research Unit (CRU))

Session 1: Informed consent and screening questionnaire for inclusion and exclusion criteria including confirmation of stage IIIb/IV CKD on 2 separate occasions in the last 6 months. All women in child-bearing age will undergo pregnancy test at this visit. In addition, all participants will complete a 7-day physical activity recall (International Physical Activity Questionnaire ¹⁵).

Session 2 (baseline measurements after overnight fast):

- Blood pressure at rest
- Endothelial cell sampling for endothelial markers of inflammation and oxidative stress (eNOS and eNOS phosphorylated at Ser 1177, NF-κB, NAD(P)H oxidase, and nitrotyrosine)
- Blood sampling for fasting lipid profile
- \bullet Blood sampling for hemoglobin A_{1C} (for participants with DM)
- Blood sampling for levels of curcumin and its metabolites
- Blood sampling for basic metabolic profile and estimated GFR including cystatin C
- Blood sampling for circulating markers of inflammation and oxidative stress (CRP, IL-6, MCP-1, and oxLDL)
- Urine sampling (random) for albumin/creatinine ratio (ACR)
- Evaluation of EDD and EID by measurements of BA-FMD and nitroglycerin-mediated dilation (NMD)
- Aortic PWV
- Assessment of vascular function in response to vitamin C (ascorbic acid) infusion
- Administer NIH Toolbox Cognitive Battery
- Start study drug after this visit

Sessions 3 and 4 (month 1 and month 3 safety visits):

- Pill count
- Safety monitoring:
 - \circ $\,$ Completion of an adverse event questionnaire
 - \circ Update medication list

Session 5 (month 6 study visit): will include the same measurements as Session 2 *except* for the NIH Toolbox Cognitive Battery. In addition, it will include the following:

- Physical activity questionnaire
- Pill count
- Safety monitoring:
 - o Completion of an adverse event questionnaire
 - Update medication list

Session 6 (month 9 safety visit): identical to Sessions 3 and 4.

Session 7 (month 12 study visit- end of study): identical to Session 2 *including* the administration of the NIH Toolbox Cognitive Battery in addition to the following:

- Physical activity questionnaire
- Pill count
- Safety monitoring:
 - Completion of an adverse event questionnaire
 - Update medication list

OUTCOME MEASUREMENTS

- **BA-FMD (primary outcome):** BA-FMD will be measured at the CRU at UIHC by a trained research assistant using high-resolution ultrasonography (GE Healthcare, Inc.) as described originally by Celermajer *et al.* ¹⁶ and by our group ¹⁷⁻²⁰. Electrocardiogram (ECG) gated end-diastolic ultrasound images and Doppler flow of the brachial artery are acquired during baseline and FMD conditions. For FMD, reactive hyperemia is produced by inflating a pediatric forearm cuff around the forearm to 250 mmHg for 5 minutes followed by rapid deflation. Endothelial independent dilation (EID) is determined by measuring brachial artery dilation for 10 minutes after administration of sublingual nitroglycerin (0.4 mg). A commercially available software package (Vascular Analysis Tools 5.5, Medical Imaging Applications, LLC, Coralville, IA) is used to acquire and analyze ECG-gated brachial artery dilation is determined as mm and % change from baseline ²¹. Doppler blood flow velocity is recorded at baseline and for 2 minutes after cuff release. Shear rate will be calculated, and if group- or condition-differences exist, BA-FMD is adjusted accordingly. *We propose to use BA-FMD as opposed to ACh-FBF since BA-FMD is less invasive and considering that BA-FMD has been utilized extensively in patients with CKD* ^{19,22-24}.

- **aPWV:** Large elastic artery stiffness will be determined by aPWV as previously described ^{19,25-27}, utilizing the Non-Invasive Hemodynamic Workstation (NIHem, Cardiovascular Engineering, Norwood, MA). The subject is supine in a quiet, dim, climate-controlled room. Blood pressure readings are obtained after 20-minute rest. A custom trans-cutaneous tonometer is placed at the carotid and femoral arteries to non-invasively assess aPWV. The distance from the supra-sternal notch to the carotid is subtracted from the distance between the two recording sites. aPWV= distance divided by time between the foot of waveforms recorded at each site. Similar to BA-FMD, the aPWV images will be analyzed by [name] group.

- **Vitamin C (ascorbic acid) infusion:** The influence of oxidative stress on BA-FMD and aPWV will be determined by infusing a supraphysiological dose of ascorbic acid (American Regent Laboratories Inc.) or isovolumic saline. A priming bolus of 0.06 g ascorbic acid/kg fat free mass (FFM) dissolved in 100 mL of saline will be infused intravenously at 5 mL/min for 20 minutes, followed immediately by a "drip-infusion" of 0.02 g/kg FFM dissolved in 30 mL of saline administered over 60 minutes at 0.5 mL/min. Vascular measurements will be made at the end of the 20-minute bolus during the "drip infusion" when peak plasma concentrations of ascorbic acid occur. The difference in BA-FMD and aPWV during ascorbic acid *vs.* saline infusion will be taken as a measure of the modulation of EDD/stiffness by oxidative stress. This technique has been developed and well established by the Seals research group ²⁸⁻³¹, which included [name]. [name] directs the Translational Vascular Physiology Lab at UIHC CRU, where several protocols that utilize vitamin C infusion are ongoing. In addition, [name], who has successfully performed and reported this technique in several clinical trials ²⁰, will remain a co-investigator for the application.

- **Systemic markers of inflammation and oxidative stress:** High sensitivity CRP, IL-6, and MCP-1 will be measured as markers of inflammation. OxLDL will be measured as a marker of systemic oxidative stress. These markers will be measured on the serum or plasma by the UIHC clinical lab.

- Endothelial cell sampling and cell protein expression: This technique performed and described by our group of investigators ^{20,30,32-34} including [name] (PI). Briefly, J-wires are advanced into a brachial artery and/or an antecubital vein and withdrawn, and cells are recovered by washing and centrifugation. Collected cells are fixed with 3.7% formaldehyde and plated on slides. After blocking nonspecific binding sites with 5% donkey serum (Jackson Immunoresearch), cells are incubated with the primary antibody. Then, cells are incubated with CY3-conjugated secondary antibodies (Research Diagnostics). Slides are systematically scanned to identify endothelial cells (positive VE-Cadherin), and nuclear integrity is confirmed using 4'.6'-diamidino-2phenylindole hydrochloride staining. Once endothelial cells with intact nuclei are identified, images are captured and then analyzed using Metamorph Software (Universal Imaging, Downingtown, PA) to quantify the intensity of CY3 staining (i.e., average pixel intensity). Values for each sample are reported as ratios of endothelial cell protein expression/human umbilical vein endothelial cell (HUVEC) to account for any variation in the staining procedure. Technicians are blinded to subject identity during the staining and analysis procedures. The following proteins will be evaluated: eNOS (BD Biosciences) and eNOS phosphorylated at Ser 1177 (BD Biosciences) as an indicator of eNOS activity ^{20,35}, NF-κB (Santa Cruz) as a marker of pro-inflammatory signaling ^{32,36}, and NAD(P)H oxidase (Upstate) ^{30,33,34} and nitrotyrosine (Abcam) ^{30,33,34} as markers of oxidative stress.

- **Cognitive function assessment:** The NIH Toolbox for the Assessment of Neurological and Behavioral Function was initiated by the NIH Blueprint for Neuroscience Research to develop state-of-the-art measurement tools to for the collection of cognitive data in large cohort studies ³⁷. The NIH Cognitive Toolbox is a validated multidimensional assessment of cognitive function domains, with minimal floor and ceiling effects, that enables us to evaluate (consistently) cognitive changes in response to our intervention ¹³. The cognitive battery of the NIH Toolbox will be administered to our patients by a trained research assistant (blinded to subject randomization) at the CRU UIHC in a quiet and private exam room over approximately 45 minutes. The following table describes the test, subdomain, and tasks that will be applied:

Subdomain	Test name and Task description
Executive function and attention	Indicate direction of central arrow when flanking arrows are pointing in the same or opposite direction. (6 minutes)
Executive function category switching	Alternate sorting according to shape or color. (7 minutes)
Working memory	Repeat the order of items (2-8) according to size in 1 category then repeat the order of items according to size in 2 categories of items. (7 minutes)
Processing speed	Identify items images (side by side) as "same" or "not the same". (2 minutes)
Episodic memory	Place pictures of individuals performing different tasks in the order they are shown. (9 minutes)
Written word pronunciation	Read printed words aloud. (6 minutes)
Auditory and word-visual picture matching	Match a single word to one of four pictures. (4 minutes)

Table 2: NIH Toolbox Cognition Battery Tests

- **Curcumin Levels:** These will be measured to evaluate the bioavailability of curcumin and its metabolites in CKD. The measurements will be conducted by [name] on a fee-for-service basis in the iC42 Laboratory in the UC-Denver Anschutz Medical Campus according to the method described by Cao *et al.* ³⁸. Curcumin (Acros Organics, Morris Plains, NJ), curcumin *O*-glucuronide and curcumin *O*-sulfate (Cell Mosaic, Worcester, MA), demethoxycurcumin and bisdemethoxy-curcumin (Sigma Aldrich), and tetrahydrocurcumin (ChromaDex, Irvine, CA) will be used in to perform liquid chromatography utilizing high-end mass spectrometry systems. The internal standard (IS) hesperetin will be purchased from 4C Pharma Scientific Inc. (ON, Canada). Heparin-treated human plasma, collected from the study participants and stored at -80 °C, will be used.

- **Clinical labs:** These include basic metabolic profile (and estimated GFR), cystatin C, ACR, Hemoglobin A_{1C}, and lipid profile will be measured by the UIHC clinical lab.

REFERENCES

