STATISTICAL ANALYSIS PLAN

NCT03223883

August 19, 2024

Statistical considerations and power calculation

BA-FMD is the primary outcome of this randomized controlled trial. The change in BA-FMD from baseline to 12 months after randomization will be compared between the curcumin and placebo groups. Other secondary outcomes include aPWV, systemic and endothelial markers of inflammation and oxidative stress, and cognitive function measured by the NIH Cognition Toolbox Battery. Power and sample size calculation ¹⁻³ is based on two-sample t-test of change in FMD by using PASS⁴. Preliminary data provides estimate of the mean and standard deviation (SD) of BA-FMD change as 1.25 and 0.88 under curcumin (n=17) and 0.08 and 0.40 under placebo (n=13), respectively. This provides a large between-conditions difference (i.e. 1.25 - 0.08 = 1.13) and effect of 1.7 taking account heterogeneity. Given the sample mean of 0.08 under control condition of usual care in Van Craenenbroeck, et al.⁵, we have assumed 0.10 as mean change in BA-FMD under placebo conditions. While there is no published literature to estimate the mean change in BA-FMD under curcumin in CKD, we believe it should be smaller than 1.25; in other words, the between conditions difference should be smaller than 1.13. Based on Van Craenenbroeck, et al. ⁵ and Thambyrajah, et al. ⁶ where the betweenconditions difference was 0.33 and 0.80, respectively, we assumed a difference of 0.6 between curcumin and placebo, considering difference between studies in intervention, study population, duration of study, and the observed difference in preliminary data. In summary we have the following assumptions: mean and SD of FMD change from baseline to 12 months after randomization are 0.70 and 0.90 under curcumin and 0.10 and 0.40 under placebo, respectively. With target power of 95% and 2-sided alpha 0.05, calculation by PASS indicates a sample size of 37 patients per group. We are going to enroll a total of 88 patients assuming approximately 18% potential loss to follow-up and equal randomization to the curcumin and placebo groups with 44 participants in each group. Power for cognitive function and other secondary outcomes: Based on the preliminary data from our pilot study of 12 weeks treatment (curcumin vs. placebo) with small sample size (17 patients per group), improved cognitive function was observed in the curcumin group but not in placebo. The effect size for episodic memory can be estimated as 0.8 for both picture sequence memory (data showed 0.77) and fluid composite (data showed 0.83). This implies that 37 patients per group will provide more than 90% power, based on calculation by PASS, with 2-sided significant level of 0.05 by using the two-sample t-test. Similarly, for other secondary outcomes, including change in aPWV and systemic and endothelial markers of inflammation and oxidative stress, 37 patients per group will provide more than 90% power if the effect size is 0.8 or larger. The power will be at least 95% if 44 patients per group can be included and effect size is 0.8.

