
Statistical analysis

Descriptive statistics will be provided for demographic characteristics, baseline measure, and outcome variables as appropriate. For example, mean and SD will be provided for continuous variables and proportion for categorical variables. 95% confidence intervals will also be provided if appropriate. We don't anticipate necessary data transformation but will confirm it before analysis.

All outcome analyses will be based on the "intent-to-treat (ITT)" principle. For Aim 1a, change in BA-FMD from baseline to 12 months after randomization will be compared between curcumin and placebo groups by using two-sample t-test. The same analysis will be performed for aPWV. As an additiaonI analysis, repeated measures analysis will be employed to compare the two groups in the change in both BA-FMD and aPWV from baseline to month 6 and 12, and the compound symmetry covariance structure will be specified. Treatment group indicator, time, and their interaction will be included as fixed effects in the model. We will explore the impact of sex, race, baseline CKD stage, and physical activity by including them as covariates in a regression model. Of note, we are stratifying by age and DM status (as noted above). For Aim 1b, repeated measures analysis will be performed for change in both BA-FMD and aPWV before and after vitamin C infusion at all three time points, the same analysis as the previous one in Aim 1a except that we now have three time points and that other covariance structures will also be explored. In addition, correlation analysis will be performed to examine the association between change in vascular function (BA-FMD and aPWV) and change in levels of inflammatory and oxidant markers including systemic measures (high-sensitivity CRP, IL-6, MCP-1, and oxLDL) and endothelial measures (eNOS and eNOS phosphorylated at Ser 1177, NF-κB, NAD(P)H oxidase,

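### Block randomisation is offered as an alternative to stratification, and no restriction within strata is stated, so balance on age, diabetes and arm size is not secured

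*Protocol*

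**What the plan says.** **Protocol, Experimental Design.** The text says that "stratified randomization will be employed based on age" (at least 55 years) and baseline diabetes status. The next sentence reads: "Block randomization is an alternative for consideration". No block size is given, no method of assignment within strata, and no other restriction such as minimisation, an urn or a biased coin.

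**Protocol, Curcumin supplementation.** A table is prepared in advance ("The randomization table will be generated by" a named person) and passed to the supplier. How it is built is not described.

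**SAP, Statistical considerations and power calculation.** The sample size rests on "equal randomization to the curcumin and placebo groups with 44 participants in each group".

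**SAP, Statistical analysis.** Stratification by age and diabetes is treated as settled, and blocking is not mentioned. The primary comparison, change in BA-FMD to 12 months, is a two-sample t-test without the stratification factors. Pooled or unequal-variance is not specified.

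**The concern.** Stratification and blocking are not rivals. Stratification keeps a separate allocation list for each stratum; blocking, or another restriction, keeps each list balanced as it fills. Separate lists of independent coin tosses are together one long list of independent coin tosses, so stratifying that way achieves nothing. A single blocked list without strata keeps the arms near equal but leaves age and diabetes to chance. Taken literally, each of the Protocol's two options gives up something the other would supply.

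Three things are at stake. A reader cannot tell how patients were allocated. The balance on age and diabetes that the Protocol evidently wants is not secured. And the primary test neither adjusts for those factors nor states how it handles unequal variances, so it leans on the allocation to keep the arms similar in size and make-up.

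**Working it through.** **Inputs from the SAP, Statistical considerations and power calculation.** Mean and SD of BA-FMD change: "0.70 and 0.90 under curcumin and 0.10 and 0.40 under placebo", a difference of 0.60. Two-sided alpha 0.05, target power 95%, 37 evaluable per group, 88 enrolled, about 18% loss.

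**Assumptions of this check.** The documents give neither stratum sizes nor a block size. Four strata (2 × 2) were simulated with shares of 25/25/25/25%, 40/40/10/10% and 45/35/12/8%, and with blocks of 4 and of 6, in 20,000 trials each.

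**1. The plan's own figure.** Welch test, 37 per group: noncentrality = 0.60 / √(0.90²/37 + 0.40²/37) = 0.60 / 0.1619 = 3.71, with about 49.7 degrees of freedom. Power is 95.29%; at 36 per group it is 94.76%. So 37 is reproduced. The equal-variance test, with SD √((0.90² + 0.40²)/2) = 0.696, gives 94.998% at 36 and 95.5% at 37. It also leads to 37, so the sample size does not reveal which test is meant. Enrolment: 37 × 1.18 = 43.66, rounded up to 44 per arm and 88 in total.

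**2. Independent 1:1 assignment, with or without strata.** The curcumin count is Binomial(88, 0.5), with SD √(88 × 0.25) = 4.69.
- P(exactly 44/44) = 8.5%.
- 95% range: 44 ± 1.96 × 4.69, or 35 to 53.
- P(39/49 or more unequal) = 34%; P(35/53 or more unequal) = 7%.
- Mean absolute difference between arms among patients of one diabetes status: about 5.2 to 5.6 patients.

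**3. Permuted blocks within the four strata.** Only the last, incomplete block in a stratum can be unequal. With blocks of 4, each stratum moves the arm count by at most 1 from half, so the total cannot be worse than 40/48.

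| Scheme | Exactly 44/44 | 95% range, one arm | Mean imbalance within one diabetes level |
|---|---|---|---|
| Independent within strata | 8.5% | 35–53 | 5.2–5.6 |
| Blocks of 4 within strata | about 43% | 42–46 | about 1.0 |
| Blocks of 6 within strata | about 37% | 42–46 | about 1.2 |

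The three sets of shares gave nearly the same results.

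**4. Effect on power (Welch, 74 completers).**
- 37/37: 95.3%.
- 29 curcumin/45 placebo: 90.8%.
- 45 curcumin/29 placebo: 97.1%.
- Averaged over independent assignment: 94.9%, so the average loss is 95.3 − 94.9 = 0.4 points.

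**5. Effect on type I error.** An 18% loss from 88 leaves 88 × 0.82 ≈ 72 completers. Simulated under no difference, with SDs 0.90 and 0.40:

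| Curcumin/placebo completers | Pooled t-test | Welch |
|---|---|---|
| 32/40 | about 7% | 5.0% |
| 40/32 | 3.6% | about 5% |

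The reason is visible at 32/40. The true variance of the difference is 0.81/32 + 0.16/40 = 0.0293. The pooled variance is (31 × 0.81 + 39 × 0.16)/70 = 0.448, which implies 0.448 × (1/32 + 1/40) = 0.0252, too small.

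**The case against.** The strongest reply is that the Protocol never says assignment within strata is unrestricted. It says stratified randomisation will be used and that a table is made in advance, which is fully compatible with permuted blocks. That stands: the figures in step 2 describe one possible reading, not the trial as conducted. A reader might infer that the trial was randomised by simple coin toss; the documents do not support this, because the table's construction is not reported.

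A reader might also infer that 44/44 is out of reach without blocks. It is not: it occurs in 8.5% of trials, and even blocks of 4 within strata reach it only about 43% of the time. The 44 per arm is a sample-size planning figure, and no exact final split is set as a requirement.

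It would likewise be too strong to say that the type I error is inflated. The direction depends on which arm is larger, the two mirror splits are equally likely under 1:1 assignment, and Welch removes the problem. The SAP plans with unequal SDs and may intend Welch. A 32/40 split can also arise from uneven dropout after perfect blocking. Chance imbalance does not bias the comparison on average, and the documents give no figure for how strongly age or diabetes predicts BA-FMD change, so the harm from imbalance on those factors cannot be sized.

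Finally, permuted blocks are not the only answer; minimisation, an urn or a biased coin would also restrict the allocation.

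What remains is that the scheme is left open in the Protocol, treated as settled in the SAP, and framed as a choice between two devices that normally work together.

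**Conclusion.** The point holds as one of specification. The allocation scheme is not fixed, and neither option as worded secures balance on both the stratification factors and arm size. Under independent assignment within strata, one arm would range from 35 to 53 (95%), against about 42 to 46 with blocks of 4 within strata. The expected cost in power is about 0.4 points; an unlucky split such as 29/45 costs 4 to 5 points, and its mirror gains about 2. The consequence for type I error arises only if the unspecified t-test is pooled. The comparison rests on the SAP's planning SDs and, for the blocked schemes, on assumed stratum shares and block sizes. It is worth correcting because the remedy costs almost nothing, not because the trial's conclusions are shown to be at risk.

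**What to change.** 1. **Protocol, Experimental Design.** State one scheme and delete the sentence offering blocking as an alternative. For example: 1:1 allocation in permuted blocks of randomly varying size within each of the four strata formed by age (under 55, 55 or over) and baseline diabetes status, with block sizes concealed from site staff. Another named restricted method, such as minimisation, would also do.
2. **SAP.** Describe the same scheme.
3. **If enrolment has started.** Do not change the scheme on paper. Report the one that generated the table, including any block sizes.
4. **Primary analysis, in either case.** Compare the 12-month change in BA-FMD in a model with treatment, age stratum and diabetes status, using an unequal-variance method (separate residual variances by arm, or heteroscedasticity-consistent standard errors). SAS 9.4, already named in the SAP, can fit this.

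The cost is a few sentences, the code for the table if it has not yet been made, and a few lines of analysis code. No extra patients, visits or procedures are needed.
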